9.2.2 Secondary

Secondary endpoint questions include:

- The distribution of HCPs' reported levels of receipt and reading of the ENJAYMO™ Physician's Guide,
- HCPs' knowledge levels for each question regarding the information included in the ENJAYMO™ Physician's Guide (i.e., all questions relating to all domains), assessed as the percentages of HCPs with correct responses to each question,
- The distribution of HCP's reported levels of dissemination of the ENJAYMO™ Patient Guide to patients treated with ENJAYMO™ (questions asked to ENJAYMO™ prescribers only),
- The distribution of HCPs' responses regarding their experience with patients' receptivity to vaccination (questions asked to ENJAYMO™ prescribers only),
- Implementation of vaccination (questions asked to ENJAYMO prescribers only), and
- The distribution of responses regarding the primary source(s) from which HCPs learned about the information included in the ENJAYMO™ Physician's Guide.

Table 9-1 Outcomes/endpoints collected in the survey

Study Objective Domains Assessed	Corresponding variable	Operational definition/derivation "Calculated as the percentage of HCPs who"*
HCPs' knowledge of the indication for ENJAYMO™ treatment in adult patients with CAD (not patients with cold agglutinin syndrome)	Knowledge that ENJAYMO™ is indicated for the treatment of hemolytic anemia in CAD patients	For question 3: "Checked" hemolytic anemia
	Knowledge that ENJAYMO™ is not indicated for the treatment of jaundice	For question 3: "Not checked" jaundice
	Knowledge that ENJAYMO™ is not indicated for the treatment of cardiac arrhythmia	For question 3: "Not checked" cardiac arrhythmia
	Knowledge that ENJAYMO™ is not indicated for the treatment of nausea and vomiting	For question 3: "Not checked" nausea and vomiting
	Knowledge that ENJAYMO™ is not indicated for the treatment of patients with cold agglutinin syndrome	For question 3: "Not checked" indicated for patients with cold agglutinin syndrome

Study Objective Domains Assessed	Corresponding variable	Operational definition/derivation “Calculated as the percentage of HCPs who”*
HCPs’ knowledge of important potential risks of serious infections from encapsulated bacteria	Knowledge that ENJAYMO™ should only be prescribed to patients who have received appropriate vaccinations, especially against encapsulated bacteria	Checked “true” to question 4
	Knowledge of current local vaccine guidelines or recommendations in patients with persistent complement deficiencies	Checked “true” to question 5
Knowledge of important potential risks of serious infections from encapsulated bacteria	Knowledge that Neisseria meningitides infection warrants caution	For question 6: “Checked” Neisseria meningitides infection warrants caution
	Knowledge that Hemophilus influenza infection warrants caution	For question 6: “Checked” Hemophilus influenza infection warrants caution
	Knowledge that Streptococcus pneumoniae infection warrants caution	For question 6: “Checked” Streptococcus pneumoniae infection warrants caution
	Knowledge that urinary tract infection warrants caution	For question 6: “Checked” urinary tract infection warrants caution
HCPs’ knowledge of the need to monitor and counsel patients	Knowledge to monitor for signs and symptoms of serious infections	Checked “yes” to question 7b
	Knowledge of caution in patients with chronic infections (Hep B, C or HIV)	Checked “yes” to question 7c
	Knowledge to counsel patients about the risks including meningitis	Checked “yes” to question 7d
	Knowledge that monitoring for kidney damage is not indicated	Checked “no” to question 7a
	Knowledge that thyroid function does not need to be assessed	Checked “no” to question 7e
	Knowledge that patients do not need to be counselled to monitor heart function	Checked “no” to question 7f
HCPs’ knowledge to counsel patients to monitor for symptoms of relevant serious infections	Knowledge to counsel patients to seek	Checked “false” to question 8c
	Knowledge that swelling in legs, ankles and feet is not a symptom of interest	Checked “false” to question 8e
	Knowledge that polyuria, dry mouth and blurred vision is not a symptom of interest	Checked “false” to question 8f
Assess whether HCPs received and read the ENJAYMO™ Physicians’ Guide	Received ENJAYMO™ Physician’s Guide	Checked “yes” to question 1
	Read ENJAYMO™ Physician’s Guide	Checked “yes” to question 2
Primary source of the indication, risk and	Response choices: SmPC, ENJAYMO™ Physician’s Guide, Professional society or	Checked each of the response choices to question 9

Study Objective Domains Assessed	Corresponding variable	Operational definition/derivation “Calculated as the percentage of HCPs who”*
recommendations for ENJAYMO™	congress, EMA website, Clinical practice guidelines, Other	

*Denominator to include “I don’t know/am not sure”

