[Preamble 1]: These questions are about the risks of serious infections and meningococcal infections associated with ENJAYMO™ (sutimlimab). Please be sure to review all response choices for each question before answering each question. Please note that you will only be able to move forward in the survey as you complete each question.

CORRECT RESPONSES ARE CHECKED ✓

1. Did you receive the “ENJAYMO™ Physician’s Guide” that provides information to minimise the risks of serious infections and meningococcal infections associated with product use?
 - Yes
 - No
 - I don’t know/am not sure

2. Did you read the “ENJAYMO™ Physician’s Guide” that provides information to minimise the risks of serious infections and meningococcal infections associated with product use?
 - Yes
 - No
 - I don’t know/am not sure

3. ENJAYMO™ (sutimlimab) is indicated in adult patients with cold agglutinin disease (CAD) for the treatment of (Check all that apply) **RANDOMIZE ORDER OF THE FIRST 5 RESPONSES**
 - Hemolytic anaemia
 - Jaundice
 - Cardiac arrhythmia
 - Nausea and vomiting
 - Cold agglutinin syndrome
 - I don’t know/am not sure

4. ENJAYMO™ (sutimlimab) should only be prescribed to patients who have received appropriate vaccinations, especially against encapsulated bacteria.
 - True
 - False
 - I don’t know/am not sure

5. Are you familiar with current local guidelines or recommendations in patients with persistent complement deficiencies for meningococcal conjugate vaccine(s), meningococcal serogroup B vaccine(s), and pneumococcal vaccine(s)?

Yes
 No
 I don't know/am not sure

6. According to the ENJAYMO™ (sutimlimab) **Summary of Product Characteristics** and the “**ENJAYMO™ Physician’s Guide**”, which of the following warrant specific caution when using ENJAYMO™ (sutimlimab)? Please select all that apply.

Neisseria meningitides infection
 Hemophilus influenza infection
 Streptococcus pneumoniae infection
 Urinary tract infection
 All of the above
 I don't know/am not sure

7. According to the “**ENJAYMO™ Physician’s Guide**”, which of the following are important activities that are necessary when using ENJAYMO™ (sutimlimab):

		Yes, needs to be monitored	No, does not need to be monitored	I don't know/am not sure
A	Monitor patients for kidney damage			

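### Read literally, Table 9-1 credits a don't-know answer on Question 3 with four of five knowledge rows and gives the catch-all answer on Question 6 none of four

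*Protocol*

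**What the plan says.** Table 9-1 (Section 9.2.2) breaks Question 3 into five rows. One is met by ticking a box: "For question 3: 'Checked' hemolytic anemia". Four are met by leaving a box blank: jaundice ("For question 3: 'Not checked' jaundice"), cardiac arrhythmia, nausea and vomiting, and "For question 3: 'Not checked' indicated for patients with cold agglutinin syndrome". In Annex 3 the question is a tick-all list ("is indicated in adult patients with cold agglutinin disease (CAD) for the treatment of (Check all that apply") with a sixth, separate don't-know option.

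The table breaks Question 6 into four rows, each met only when the named option is ticked. The fourth is "Knowledge that urinary tract infection warrants caution". Annex 3 adds two further options to that question, "All of the above" and don't know. Neither has a row.

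The protocol's only rule for don't-know answers concerns the denominator. The table footnote reads "Denominator to include “I don’t know/am not sure", and Section 9.9.1.1 repeats the rule. Section 9.2.1 places both questions in the six-question core set, with Question 3 as the only question on the indication. Section 9.9.1.2 builds the composite from the percentage correct on each item, weighted by its denominator, and sets it against 80%.

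**The concern.** A row that is met by a blank box cannot separate a respondent who rejected the option from one who gave no substantive answer. Someone who says they do not know the indication is recorded as knowing that the product is not indicated in cold agglutinin syndrome, which is the distinction this domain is meant to test. On Question 6 the fault runs the other way: the answer that agrees with the whole key is scored the same as don't know.

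Don't-know answers are plausible here. The survey admits physicians who have not yet prescribed (Section 9.4), and Section 9.7 expects possibly 10 prescribers among 50 respondents. If those who did not read the Guide choose don't know more often, the planned comparison of readers with non-readers would be narrowed on the Question 3 rows.

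**Working it through.** **Inputs**
- Scoring key: Table 9-1. Response options: Annex 3. Weighting: Section 9.9.1.2.
- Core rows in Table 9-1, Questions 3 to 8: 5 + 1 + 1 + 4 + 6 + 3 = 20. Only three Question 8 rows are legible in the text reviewed, and one looks broken. Annex 3 lists six parts; if all six are scored the total is 23. Both totals are carried.
- Response shares: not given in the protocol. They are assumptions, shown from 10% to 30%.

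**The plan's own figure.** Section 9.7 gives a precision of 11.1% at n = 50 and 80% knowledge: 1.96 × √(0.80 × 0.20 / 50) = 0.1109. It reproduces and is not in dispute. It serves only as a yardstick.

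**Step 1: score each response pattern by the key as written**

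| Response | Rows met |
|---|---|
| Q3: hemolytic anaemia only | 5 of 5 |
| Q3: hemolytic anaemia and cold agglutinin syndrome | 4 of 5 |
| Q3: don't know only | 4 of 5 |
| Q6: four options ticked singly | 4 of 4 |
| Q6: catch-all only | 0 of 4 |
| Q6: don't know only | 0 of 4 |

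**Step 2: effect on a single row.** Let a share d answer don't know on Question 3 and everyone else be fully right. Each blank-box row then reads (1 − d) + d = 100%, where 1 − d have shown knowledge. At d = 30% the row reads 100% instead of 70%. On Question 6, if a share d use only the catch-all and the rest tick all four boxes, each row reads 1 − d, or 70% instead of 100% at d = 30%.

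**Step 3: effect on the composite.** Assume every respondent answers every item, so denominators are equal. Let f be the share giving the answer in question.
- Item-weighted: f × 4/20 or f × 4/23, upward for Question 3 and downward for Question 6.
- Equal question weights with partial credit: f × (4/5)/6 upward for Question 3; f × 1/6 downward for Question 6.
- Equal question weights, all parts required: 0 for Question 3; f × 1/6 downward for Question 6.

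| Composite shift, points | f = 10% | f = 20% | f = 30% |
|---|---|---|---|
| Q3, 20 items | +2.0 | +4.0 | +6.0 |
| Q3, 23 items | +1.7 | +3.5 | +5.2 |
| Q3, equal weights, partial credit | +1.3 | +2.7 | +4.0 |
| Q3, all parts required | 0 | 0 | 0 |
| Q6, 20 items | −2.0 | −4.0 | −6.0 |
| Q6, 23 items | −1.7 | −3.5 | −5.2 |
| Q6, equal weights (either rule) | −1.7 | −3.3 | −5.0 |

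**Step 4: after correction.** Don't know on Question 3 falls from 4 of 5 to 0 of 5. The catch-all on Question 6 rises from 0 of 4 to 4 of 4. A respondent who answers don't know throughout goes from 4/20 = 20.0% (or 4/23 = 17.4%) to 0%. A fully correct respondent who used the catch-all goes from 16/20 = 80.0% (or 19/23 = 82.6%) to 100%.

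**The case against.** The strongest objection concerns the scoring unit. Section 9.2.1 and the Synopsis describe the composite in terms of correct responses to questions, and the Synopsis analysis text speaks of answering all the core questions correctly. If Question 3 is right only when every part is right, a don't-know answer fails on hemolytic anaemia and the over-credit never reaches the composite. This stands as a limit on size: Section 9.9.1.2 supports item-level scoring but does not settle it. The separate rows of Table 9-1 stay wrong either way.

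Second, keeping don't-know answers in the denominator suggests they were meant to count as not correct, and mapping a catch-all to its components is an ordinary derivation step that a SAP or the survey programming could supply. That has force for Question 6, where the table has no rule for the option and an analyst would probably add one. It has less for Question 3, where the protocol itself fixes the blank-box rule and following it gives the wrong result.

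Three stronger readings are tempting but unsupported:
- If everyone answered don't know on Question 3, its five rows would average (0 + 4 × 100)/5 = 80%, the same number as the success target. No section tests an average of the Question 3 rows against 80%, and the hemolytic anaemia row would read 0%, so the failure would be visible.
- A reader might infer that Table 9-1 and Annex 3 disagree on urinary tract infection. The marks showing correct answers to Questions 3 to 6 are not visible in the text reviewed, so no conflict can be shown. Whether that option belongs in the key cannot be judged without the Physician's Guide.
- That Question 6 has no wrong option under this key is a matter of item design, not a scoring error.

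**Conclusion.** The point holds for the item-level results. Applied literally, Table 9-1 credits four of five Question 3 rows to a respondent who says they do not know, and none of four Question 6 rows to one who picks the answer agreeing with the whole key. These counts need no assumption beyond reading the table as written.

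The effect on the primary composite is conditional. Per assumed 10% of respondents, Question 3 adds 1.7 to 2.0 points under item weighting, 1.3 with equal question weights and partial credit, and nothing if all parts are required. Question 6 subtracts 1.7 to 2.0 points whichever unit is used. At an assumed 30%, item weighting gives 5.2 to 6.0 points in either direction, about half the planned 11.1-point precision. The two errors run in opposite directions and cannot be relied on to cancel. It does not follow that the composite is certain to be biased, or biased upward. This should be fixed before database close; it does not undermine the study.

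**What to change.** In Table 9-1, state that a don't-know answer is not correct on any row of its question, and that a blank-box row of Question 3 counts as correct only if the respondent ticked at least one substantive option. Score the Question 6 catch-all as all four options ticked, or delete it from Annex 3. If the survey is not yet live, make don't know an exclusive choice on the Question 3 page.

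The cost is a few lines in Table 9-1 and, before launch, a small programming change. If the survey is already running, the scoring rules alone are enough, provided each tick is stored. They need to be fixed before database close because Section 9.8 rules out going back to respondents about knowledge answers.

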9.2.1 Primary

The primary endpoint is knowledge levels of key information included in the ENJAYMO™ Physician's Guide across these 4 domains (assessed by 6 questions):

- Indication for CAD patients only (question 3)
- Important potential risks of serious infections including meningococcal infections (questions 4 and 6)
- Recommendations for vaccination of patients as per local regulations (question 5)
- Recommendations for monitoring and counseling patients to promote real-world safe-use conditions (questions 7 and 8).

The primary endpoint is a composite endpoint based on the percentages of HCPs with correct responses to questions included in the composite. The composite is the weighted average knowledge level across the core question set (6 questions) from the above domains. Success

criteria for the primary endpoint percentage is at least 80% of HCPs have answered the item correctly (if the number of HCPs who answered is at least 30).

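### Questions 4, 5 and 6 are keyed only to agreement, so agreeing with everything earns full marks on the risk and vaccination domains of the primary endpoint

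*Protocol*

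**What the plan says.** Section 9.2.1 of the protocol assigns the six core questions to four domains. Two questions carry the risk domain, listed as "Important potential risks of serious infections including meningococcal infections (questions 4 and 6". The vaccination domain has a single question and is listed as "Recommendations for vaccination of patients as per local regulations (question 5". Question 3 covers the indication, while questions 7 and 8 cover monitoring and counselling.

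The composite is a weighted average over these questions, with a success threshold of 80%.

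Table 9-1 (section 9.2.2) gives the answer key.

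- **Question 4** is a single statement that the product "should only be prescribed to patients who have received appropriate vaccinations, especially against encapsulated bacteria". The scoring rule is "Checked “true” to question 4".
- **Question 5** is keyed *true* in Table 9-1. In Annex 3 it asks whether the respondent is familiar with local vaccination guidance and offers yes, no or don't know. The labels differ, but the key is affirmative either way.
- **Question 6** asks "which of the following warrant specific caution when using ENJAYMO™ (sutimlimab)? Please select all that apply". Table 9-1 has four rows for it, all keyed *Checked*, including "Knowledge that urinary tract infection warrants caution". The only other options in Annex 3 are *All of the above* and *I don't know/am not sure*.

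The other three questions do contain wrong options. Table 9-1 keys four of the five options in question 3 as *Not checked*, items a, e and f of question 7 as *no*, and items c, e and f of question 8 as *false*.

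**The concern.** A knowledge item measures knowledge only if someone without it can be expected to get it wrong. In questions 4 to 6 the sole way to lose a mark is to disagree, leave an option unticked or admit uncertainty. Someone who says yes to everything loses nothing. Annex 3 adds a cue: the preamble to the main survey tells respondents that the questions concern the risks of serious and meningococcal infection. Question 5 goes further, since it asks for self-rated familiarity and tests no fact.

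These three questions make up the domains on infection risk and vaccination, which sections 4 and 7 give as the main reason for the Guide. At stake is whether a high score there, and the share of the composite it supplies, can be read as evidence that the Guide works.

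**Working it through.** **The plan's own figures.** The protocol gives no figure for the effect of the answer key. Its stated precision at 50 respondents and 80% knowledge reproduces: 1.96 × √(0.8 × 0.2 / 50) = 11.1 percentage points (section 9.7). That describes sampling error only and does not cover a one-directional key.

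**Inputs.** The key comes from Table 9-1. For items a, b and d of question 8 it comes from Annex 3, which marks them *True*. The domains come from section 9.2.1. The test case is a respondent who affirms every substantive option.

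| Question | Domain | Items | Keyed to agreement | Score if all affirmed |
|---|---|---|---|---|
| 3 | Indication | 5 | 1 | 1/5 |
| 4 | Risks | 1 | 1 | 1/1 |
| 5 | Vaccination | 1 | 1 | 1/1 |
| 6 | Risks | 4 | 4 | 4/4 |
| 7 | Monitoring and counselling | 6 | 3 | 3/6 |
| 8 | Monitoring and counselling | 6 | 3 | 3/6 |
| Total | | 23 | 13 | 13/23 |

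**By domain.**

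- Indication: 1/5 = 20%.
- Risks: (1 + 4)/(1 + 4) = 100%.
- Vaccination: 1/1 = 100%.
- Monitoring and counselling: (3 + 3)/(6 + 6) = 50%.

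**Overall, under three possible scoring rules.**

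- Each question all-or-nothing: questions 4, 5 and 6 are right, so 3/6 = 50%.
- Items pooled: 13/23 = 56.5%.
- Equal-weight mean of question fractions: (0.2 + 1 + 1 + 1 + 0.5 + 0.5)/6 = 4.2/6 = 70%.

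The two 100% domain scores are the same under all three rules.

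**What the other questions must achieve.** Suppose questions 4 to 6 all reach 100% and the six questions have equal denominators. The average needed on questions 3, 7 and 8 for an 80% composite is (6 × 0.8 − 3)/3 = 1.8/3 = 60%. If the 23 items are pooled instead, questions 4 to 6 supply 6 of them, and the other 17 need (0.8 × 23 − 6)/17 = 12.4/17 = 72.9%. The allowance depends on the weighting, but in both cases it lies below 80%.

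**Effect of two wrong options in question 6.** With two added options keyed *Not checked*, the same respondent scores 4/6 on question 6 and (1 + 4)/(1 + 6) = 5/7 = 71.4% on the risk domain, before any change to question 4.

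**The case against.** The strongest reply is that the instrument as a whole penalises indiscriminate agreement. Questions 3, 7 and 8 contain ten reverse-keyed items, and uncertain answers count in the denominator. Every question is also reported separately as a secondary endpoint, and section 9.9.1.2 stratifies by whether the Guide was read. Inflated results on questions 4 to 6 would therefore be visible next to the others. All of this is true, and it limits the harm. It does not take the bias out of the composite, which is what is compared with 80%. The safeguards in section 9.8 (randomised response order, one sitting, no revision of answers) do not offset a key that runs one way.

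Two stronger readings are tempting, and neither is supported.

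- *Agreement alone passes the 80% target.* It does not: the pure agree-with-everything respondent scores 50% to 70%. A respondent who answers question 3 fully correctly and agrees with everything else would reach (1 + 1 + 1 + 1 + 0.5 + 0.5)/6 = 83.3%, but only with partial credit and equal question weights. Pooling items gives the same person 17/23 = 73.9%, and all-or-nothing scoring gives 4/6 = 66.7%. The protocol does not fix the rule that yields 83.3%.
- *Urinary tract infection was meant as the wrong option and its key is reversed.* Table 9-1 does file it under a heading about encapsulated bacteria. However, sections 4 and 7 speak of serious infections generally and only single out encapsulated-bacteria and meningococcal infections, so other infections are not excluded. The Guide and the product information are not at hand. The tick marks for questions 3 to 6 in Annex 3 are not legible in the copy reviewed, so the key rests on Table 9-1, which is explicit.

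**Conclusion.** The point holds as a weakness of measurement in the primary endpoint. Questions 4, 5 and 6 are keyed only to agreement, and question 6 has no substantive wrong option. Agreement alone therefore gives 100% on two of the four primary domains under any of the scoring rules considered. The bias is upward on these three questions; it does not run one way across the whole instrument. With equal denominators and questions 4 to 6 at 100%, a 60% average on the remaining three is enough for the target. That figure is the limiting case, since the protocol gives no basis for saying how many respondents would answer by agreement.

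The count of two domains follows section 9.2.1. Table 9-1 groups questions 4 and 5 under one risk heading, which does not change their key. Because the remedy is cheap and follows what question 3 already does, the change is worth making.

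**What to change.** - **Question 6:** add at least two options for which the Guide does not ask for caution, keyed *Not checked* as in question 3, and remove *All of the above*.
- **Question 4:** recast as a multiple-choice item with wrong alternatives.
- **Question 5:** replace the self-rated familiarity question with a knowledge item that can be answered wrongly, or report it outside the composite. Without this, the vaccination domain stays untested whatever is done to the other two.
- **Urinary tract infection row:** reconcile it with its heading in Table 9-1 and with the Guide, without presuming the key is reversed.
- **If fielding has begun** (section 6 plans a start in Q2 2024): keep the items, because section 9.1.1 requires any second wave to use the same survey. Report the composite also without questions 4 to 6, noting that this version covers only indication and monitoring and counselling.

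The cost is rewording in Table 9-1 and Annex 3, then translation into German, Italian and Dutch with the independent proof-reading and signed affiliate approval that section 9.1.2 requires. The observed knowledge level may be lower. For data already being collected, the cost is one additional summary.
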